7.4 Reporting Procedures

Once staff members report an AE or SAE to MPIs, [name] or [name] (and only [name] in Phase 3, as she is not blind in Phase 3) will code severity, causal relationship, and whether the event was expected. If necessary, she will seek further information from the participant or parent or other source before coding.

AEs will be coded on a weekly basis. Any potential SAE will be immediately reviewed by one of the MPIs (or a qualified designee in her absence) and coded; this coding will subsequently be reviewed by the SMC (Safety Monitoring Committee). Coding of AEs and SAEs occurs on a study AE case report form.

SAEs that are unanticipated, serious, and possibly related to the study intervention will be reported to the Safety Monitoring Committee (SMC), IRB, and NCCIH in accordance with requirements. We will use the Butler Hospital IRB-approved AE report form.

- Unexpected fatal or life-threatening SAEs related to the intervention will be reported to the IRB, NCCIH Program Officer, and SMC within 3 days of the investigator becoming aware of the event. Other serious and unexpected SAEs related to the intervention will be reported within 7 days. These timeframes follow guidance from NCCIH and are consistent to local IRB policies.

Anticipated or unrelated SAEs will be handled in a less urgent manner but will be reported to the SMC, IRB, and other oversight organizations in accordance with their requirements, and will be reported to NCCIH on an annual basis.

- Unrelated SAEs that are fatal or life threatening must be reported to the Butler Hospital IRB within 7 days of the investigator becoming aware of the event.
- Unrelated SAEs that are not fatal or life-threatening must be reported to the Butler Hospital IRB annually.

All other AEs documented during the course of the trial will be reported to NCCIH on an annual basis by way of inclusion in the annual report and in the annual AE summary which will be provided to NCCIH and to the SMC. The SMC Report will state that all AEs have been reviewed.

7.5 Follow-up for Adverse Events

Any SAEs related study participation will be followed for outcome information until resolution or stabilization. Follow-up reports will be submitted to the IRB, SMC, or NCCIH as required in each specific instance.

7.6 Safety Monitoring

The NCCIH requires that all Human Subjects research studies undergo independent monitoring, and NCCIH Program Officials will provide specific guidelines to the PI for the study.

8. INTERVENTION DISCONTINUATION

Adolescents will be discontinued from an intervention in the following circumstances:

- If a parent, the adolescent, their primary care provider, or their mental health provider does not believe it is in the best interest of the adolescent to continue. As soon as an MPI is informed of this, she will speak with the participant about discontinuation. There may be circumstances (e.g., worsening depression, an injury in yoga class) when the MPI reaches out to a primary care provider, MH provider, or parent to actively inquire if they have concerns about the adolescent continuing to participate.
- If a parent or adolescent choose to discontinue the adolescent's attendance.
- If one of the MPIs, in consultation with the relevant instructor or therapist, finds the adolescent to be so disruptive to the rest of the class that they have a repeated and substantive negative impact on the other participants.
- If the adolescent does not or is unable to follow guidelines regarding being in a private space when participating in the video-based intervention.

Participants will continue with subsequent assessments with their (parent and adolescent) permission. Assessment schedule and assessments used will not change.

9. STATISTICAL CONSIDERATIONS

9.1 General Design Issues

Our primary overall objective for this pilot project is to develop procedures and manuals, and acquire supportive data on feasibility and acceptability that will prepare us to conduct a fully-powered non-inferiority design trial of hatha yoga vs. group CBT for depression in adolescents.

Because this is a treatment development study, we have chosen our sample sizes as being sufficient to assess feasibility and acceptability. This study is not powered to assess differences (or non-inferiority) between treatments.

9.1.1 Summary of Aims, Endpoints, and Data Analytic Strategy.

Table 4 summarizes each aim, the target endpoint, and the data analysis strategy, where applicable.

Table 4. Summary of Aims, Endpoints, and Analyses.

| Aim/Objective | Endpoint | Analyses |
|---|--|--|
| Phase 1 – Focus Groups | | |
| Conduct focus groups with adolescents and parents | Conducted up to 4 focus groups with adolescents and parents | Qualitative analysis – see description below. |
| Solicit feedback from experts in depression, health, and/or yoga in adolescents | Feedback received from experts in relevant areas | Qualitative analysis – see description below. |
| Create a manual, training materials, and fidelity assessment scale for instructors | Draft instructor manual, instructor training materials, and fidelity assessment scale created | N/A |
| Phase 2 – Open Trial | | |
| Pilot the yoga intervention | 12 adolescents enrolled & follow up assessments completed | N/A |
| Assess feasibility, acceptability, and safety of both the yoga intervention and the comparison group | See Table 5 for a complete list. | Descriptive statistics for feasibility, acceptability, and safety. See Table 5. |
| Via structured interview, elicit feedback from adolescents, parents, and yoga instructors | Revise draft of instructor manual, instructor training materials, and fidelity assessment scale | Qualitative analysis – see description below. |
| Phase 3 – Pilot RCT, Study A and B | | |
| Pilot RCT of hatha yoga vs. group CBT for depression | 34 adolescents enrolled & follow up assessments completed (plus any Study B participants) | N/A |
| Assess feasibility, acceptability, and safety of both the yoga intervention and the comparison group ** This is primary ** | See Table 5 for a complete list (Endpoints examined separately for main participants and study B participants; also examined separately for participants consented pre-COVID and post-COVID) | Descriptive statistics (see Table 5) and qualitative data analysis |
| Assess within-group changes on outcomes. The primary outcome will be depression symptom severity at post-intervention (M3). Secondary outcomes include depression severity at follow-up (9 months), and self-report of depression, functional impairment, anxiety, and sleep at post-intervention (M3) and 9 months. ** This is exploratory ** | Endpoint = post-intervention (M3) (Endpoints examined separately for main participants and study B participants; also examined separately for participants consented pre-COVID and post-COVID) | Within-subjects t-tests (e.g., from pre-intervention to post-intervention/M3). We will conduct analyses separately by treatment group. We will calculate effect sizes (Cohen's d) from pre- to post-treatment/M3, with corresponding confidence intervals. |
| Assess within-group changes on self-compassion and meta-cognitive awareness ** This is exploratory ** | Endpoint = post-intervention (M3) (Endpoints examined separately for main participants and study B participants; also examined separately for participants consented pre-COVID and post-COVID) | Within-subjects t-tests (e.g., from pre-intervention to M3). We will conduct analyses separately by treatment group. |

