1. STUDY OBJECTIVES

1.1 Primary Objective

Our primary overall objective for this pilot project is to develop procedures and manuals, and acquire supportive data on feasibility and acceptability that will prepare us to conduct a fully-powered non-inferiority design trial of hatha yoga vs. group CBT for depression in adolescents.

Our proposed project will have three phases. Specific Aims for each phase include:

Phase 1: Initial Development

1. Conduct separate focus groups with depressed adolescents (n=24) and parents (n=24) to ascertain their feedback on ways to make yoga classes an acceptable and feasible intervention;
2. Solicit feedback from experts in depression, health, and/or yoga in adolescents;
3. Create a manual, training materials, and fidelity assessment scale for instructors.

Phase 2: Open Trial

4. Pilot the yoga intervention in a sample of 12 adolescents;
5. Via structured interview, elicit feedback from adolescents, parents, and yoga instructors; use the feedback to further refine the yoga manual and other related materials.

Phase 3: Pilot RCT (Study A)

6. Conduct a pilot randomized clinical trial (n = 34) of 3 months of hatha yoga vs. group CBT for depression for adolescents aged 13-18 with major depression; we also refer to this as Study A. [Note. There will also be a Study B in which we may enroll up to an additional 20 adolescents that do not meet Phase 3 (Study A) inclusion criteria due to either low depression severity on the QIDS or recent changes in treatment. Study B will run concurrent to Phase 3/Study A. Participants will undergo the same procedures as the main Phase 3 participants. Allowing these individuals to participate will allow us to increase the size of the yoga/CBT classes, potentially making them of more value for all participants.]
7. Assess feasibility, acceptability, and safety of both the yoga intervention and comparison group;
8. Assess within-group changes on outcomes. The primary outcome will be adolescent report of depression symptom severity at 3 months, assessed by a blind evaluator. Secondary outcomes include depression severity at follow-up (9 months), and self-report of depression, functional impairment, and anxiety at 3 and 9 months.

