- d) Adolescents must be medically cleared for moderate physical activity by their primary care physician. This criterion may be met by a current (dated in the past year) statement from their pediatrician that the adolescent may participate in school or camp programs including physical education.
- e) Adolescents must be able to read and write English sufficient to complete informed consent and engage in interventions.
- f) Adolescents aged 13-17 must assent to be in the study, and their parent/legal guardian must consent to their participation. Adolescents aged 18 must consent to be in the study.
- g) Able to attend one of the class times.
- h) Access to a private space in their home for study classes, and a device that will support use of the video platform we are using to conduct assessments and classes.

Parent Inclusion Criteria for all Phases

- a) Parent/legal guardian of an adolescent who is eligible for the study.
- b) Provides informed consent.
- c) Able to read and write English sufficient to complete informed consent and study questionnaires.

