In Phase 2, once we have medical clearance to participate in physical activity from a participant, and talk with the participant to confirm their interest, they are considered "enrolled." Enrollment may occur at the BL visit or at a separate BL2 phone call (if there is a need to request and wait for medical clearance). BL2 must occur within 14 days of BL1.

In Phase 2, adolescents are invited to attend classes within a week after enrollment.

Randomization occurs in Phase 3 only. Randomization will occur at a BL2 phone call. Participants are considered enrolled at BL2 after randomization. Adolescents invited to begin the study intervention within a week after enrollment.

Documentation of Reasons for Ineligibility

All participants who express interest in the study (i.e., make contact with us regarding the study) will be tracked in a separate database along with the status of their participation. Any participant who is screened by phone for any aspect of the study including Phase 2, Phase 3 Study A, and Phase 3 Study B (even if only one inclusion criterion is assessed before the participant is determined not eligible) will have a study record documenting which inclusion criteria were assessed and the outcome of that assessment (i.e., as part of a study log). The study record is linked to the participant's name and other personal identifiers only by the study ID number. Once study

status is determined (i.e., determination that a person is not eligible and the reason), we will not retain the names of potential participants if they have not signed a consent form.

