5. STUDY INTERVENTIONS

5.1 Interventions, Administration, and Duration

Yoga classes are administered to a group of participants. Participants attend classes once per week; they will also be asked to practice yoga at home. Classes will take place in a room on the Butler Hospital campus; they are planned to be 45 minutes long. Registered yoga teachers will deliver the intervention. Potential risks include loss of privacy or breach of confidentiality, increased distress due to procedures, ineffective intervention (i.e., lack of improvement in depression symptoms), and mild physical injury.

Group CBT is administered to a group of participants. Participants attend groups once per week; they will also be given homework assignments. Classes will take place in a room on the Butler Hospital campus. Therapists will have a master's degree or Ph.D. in psychology or a related field (e.g., social work). Potential risks include loss of privacy or breach of confidentiality, increased distress due to procedures, and ineffective intervention (i.e., lack of improvement in depression symptoms).

COVID Modifications

In the event we are unable to hold in-person classes (i.e., due to a major public health emergency), we will hold classes via videoconference. This would be through the use of HIPAA-compliant videoconference service.

We will send information about accessing the videoconference to participants via email, according to preferences for method of contact indicated by participants/ parents/guardians during the baseline consent process.

For participants who began study prior to COVID modifications (and therefore had an opportunity to switch to remote participation after consenting to and participating in in-person participation): Prior to sending out video links and holding video-based classes, we will conduct telephone consent / assent for remote participation with parents and teens, and document that they understand risks and benefits of remote participation, and consent/ assent to participate. We will use an IRB-approved script to do this. Any participants who have already consented to receiving REDCap links via email will also be asked if they would like to receive a REDCap link that will bring them to a written version of that oral consent script, so that they may follow along with the consent.

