5.2 Handling of Study Interventions

Yoga Intervention

Yoga classes. The manualized hatha yoga program will begin with a 30-minute initial

individual session with a yoga teacher, to introduce the participant to yoga and give them a chance to privately ask any questions or express any concerns. In this individual session, teachers will focus on how to practice yoga in a way that is physically safer, and review signs that a participant should alter or back out of a pose.

Subsequently, participants will be asked to attend one 45 minute class per week for 12 weeks. Each class will consist of: introduction of a theme; pranayama (breathing practices); standing postures (asanas); floor postures; inversions; guided savasana (relaxation); and home practice assignments. Classes will emphasize breath-linked movement and moderate physical activity. Class size will range between 1 and 12 participants.

Yoga Home Practice. Home practice will be essential for increasing yoga “dosage.” When participants first start class, we will give them a yoga mat to take home. In each class, the yoga instructor will review specific practices and recommend that participants try those practices at home. The practices will always be ones that carry with it minimal risk of injury, and instructors will go over safe practice in class. Sample practices that may be introduced for homework include: 3-part breath, a cat-cow-child sequence, and a half sun salutation. Participants may continue in the study regardless of whether they practice at home.

Yoga Instructors. The Yoga Alliance is a professional organization which sets standards for yoga teacher training. One can be a Registered Yoga Teacher (RYT) at the 200- or 500-hour level. Experienced Registered Yoga Teachers (E-RYT) at the 500-hour level have at least 4 years of experience and 2000 hours teaching, and are qualified to train teachers and provide continuing education. We will require that all study yoga teachers be RYT^s and will have previous experience working with adolescents. Teachers will also have study-specific training on research methods, working with depressed adolescents, and the yoga manual. They will meet approximately monthly for supervision. There will be at least 2 trained yoga teachers. Yoga supervisors will also review audio recordings of classes to assess instructor adherence.

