9.6 Data Analyses

Qualitative Data Analysis

Focus groups (Phase 1) or interviews (Phase 2, 3) will be recorded and transcribed. We will use a template organizing style to analyze qualitative data [34]. [name] will oversee the process. She will develop an initial codebook with *deductive* codes. *Inductive* codes capturing emergent themes will arise from team-level review of the transcripts. Once the codes are developed, members of the scientific team will independently code remaining transcripts; 20% of transcripts will be double coded and reviewed to ensure coding fidelity. Information gleaned will then be reviewed by the scientific team and used to modify manuals and procedures.

Quantitative Data Analysis

In Phase 2 and Phase 3, we will use descriptive statistics to summarize all variables. We will also conduct exploratory analyses of change over time in depression (which will be the primary outcome in an efficacy study), impairment and anxiety (which will be secondary outcomes) and potential mechanisms of action. All variables will be examined and tested for distributional assumptions prior to statistical analysis. We will use within-subject t-tests, separated by treatment group. In this study, these analyses should be considered exploratory. Any data that violates statistical assumptions will either be transformed accordingly and appropriate statistical tests will be applied (e.g., non-parametric approaches such as the Wilcoxon signed rank test in lieu of t-tests). We will look at outcomes for the entire group of enrolled participants for Phase 2 and Phase 3. In addition, in Phase 3, we will examine outcomes for 2 sets of subgroups:

- c. Study A vs. Study B
- d. Pre-COVID enrollment (including those who participated in some in-person and some video classes, which is the majority of the Pre-COVID enrolled group) vs. Post-COVID enrollment (i.e., those who consented and started video-based classes from the start).

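### Both treatments are taught in shared classes, but the exploratory within-arm t-tests and confidence intervals assume independent teens, so the intervals are too narrow if class-mates' changes are positively correlated.

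*Combined protocol and SAP*

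**What the plan says.** Section 5.1 describes both arms as group treatments: "Yoga classes are administered to a group of participants" and "Group CBT is administered to a group of participants". Section 5.2 gives the same size range for each: "Class size will range between 1 and 12 participants". It also requires at least two trained yoga teachers and at least two trained CBT therapists, without saying how they are allocated to classes. Study B teens join the same classes. Section 1.1 gives the reason: "Allowing these individuals to participate will allow us to increase the size of the yoga/CBT classes".

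The number of class times per arm is not stated. Section 4.1 implies that there may be more than one ("Able to attend one of the class times"). Entry is rolling rather than in closed cohorts; section 4.3 says "Adolescents invited to begin the study intervention within a week after enrollment".

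On analysis, section 9.6 says "We will use within-subject t-tests, separated by treatment group". Table 4 repeats the t-tests and adds Cohen's d "from pre- to post-treatment/M3, with corresponding confidence intervals". Section 9.2.1 mentions confidence intervals for key outcomes without giving a method. The only assumption checks in section 9.6 are distributional. No section mentions a class or instructor term, a class-level ICC, robust standard errors, or a caveat about clustering.

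**The concern.** A paired t-test deals with the correlation between a teen's own two scores. It still assumes that one teen's change is independent of another's. Teens who share a class, an instructor and a peer group may improve or stall together. The mean change in an arm then carries less information than its head count suggests, and an interval built on the head count is too short.

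The protocol itself allows that the group matters. It hopes that larger classes will be worth more to everyone in them (section 1.1), it lets a teen be removed for harming the experience of others (section 8), and it measures group cohesion after the first class and at Month 3 (Table 2). Assuming zero class correlation without saying so sits poorly with that.

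At stake is how firm the exploratory within-arm gains appear. One of them is QIDS change from baseline to Month 3, which section 9.5.2 marks as the primary outcome of a later efficacy study.

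**Working it through.** The plan has no power, precision or design-effect figure to reproduce. The 34 in Study A were chosen for feasibility and acceptability (sections 9.1 and 9.2.1).

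**Inputs from the documents.** Study A has 34 teens; class size is 1 to 12; the targets are 3 enrolled per month and 80% completing Month 3 (Table 5); treatment lasts 12 weeks.

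**Assumptions.** Allocation is 1:1, which even block sizes suggest, so 34/2 = 17 per arm. Intervals are two-sided 95%. The ICC of change scores among class-mates is 0.02 to 0.10; the only ICC in the documents concerns rater reliability (section 10.3.3).

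**Cluster size m.** This is the number of analysed teens sharing a class.
- Concurrent membership: 12 weeks is 84/30.4 = 2.76 months, and 3 × 2.76 = 8.3 teens are in treatment at once, about 4 per arm.
- Two persistent class times per arm: 17/2 = 8.5.
- One persistent class time per arm: 17. This exceeds the stated maximum of 12, so it applies only if everyone who ever passes through that class time counts as one cluster.

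**Formulas.** Design effect DE = 1 + (m − 1) × ICC. The standard error should be multiplied by √DE. The unadjusted half-width in SDs of change is t(0.975, 16)/√17 = 2.120/4.123 = 0.514.

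| m | ICC | DE | √DE | Half-width (SD of change) |
|---|---|---|---|---|
| 4 | 0.02 | 1.06 | 1.03 | 0.53 |
| 4 | 0.05 | 1.15 | 1.07 | 0.55 |
| 4 | 0.10 | 1.30 | 1.14 | 0.59 |
| 8.5 | 0.02 | 1.15 | 1.07 | 0.55 |
| 8.5 | 0.05 | 1.375 | 1.17 | 0.60 |
| 8.5 | 0.10 | 1.75 | 1.32 | 0.68 |
| 17 | 0.02 | 1.32 | 1.15 | 0.59 |
| 17 | 0.05 | 1.80 | 1.34 | 0.69 |
| 17 | 0.10 | 2.60 | 1.61 | 0.83 |

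At 80% retention, 0.80 × 17 = 13.6, about 14 completers per arm. The unadjusted half-width is then 0.58. Two class times would hold 7 completers each: DE is 1 + 6 × 0.02 = 1.12 to 1 + 6 × 0.10 = 1.60, and √DE is 1.06 to 1.26.

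**Coverage of the unadjusted interval.** This was simulated with 14 completers, normal data, a random class effect and 100,000 runs per setting. The nominal level is 95%.

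| Classes | ICC 0.01 | ICC 0.05 | ICC 0.10 |
|---|---|---|---|
| 4, 4, 3, 3 | 94.8% | 93.6% | 92.2% |
| 5, 5, 4 | 94.7% | 93.1% | 90.8% |
| 12, 2 | 94.1% | 89.5% | 84.0% |
| one class of 14 | 93.6% | 87.4% | 80.0% |

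At ICC 0, coverage is 95%. With one class per arm, no within-arm model can estimate the class effect, so only an assumed ICC can be used.

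**The case against.** The strongest case against the point is that little depends on these intervals. Table 4 and section 9.6 call the analyses exploratory. Feasibility, acceptability and safety are primary, and sections 9.1 and 9.2.1 disclaim power for efficacy or non-inferiority. All of that stands, and it limits the weight of the point. It does not make a nominal 95% interval cover 95%.

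A reader might infer that these intervals will set the sample size or margin of the full trial. The documents do not say so. They name procedures, manuals and feasibility and acceptability data as what the pilot contributes, and no rule uses the within-arm d or its interval.

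A reader might also infer that the intervals are certainly, or badly, too narrow. That is not supported either. The ICC is not given and could be near zero. Rolling entry means overlapping memberships, at the target rate about 4 Study A teens per arm at once, where the effect is small. The largest figures need a single cluster that persists throughout.

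On the other side, the figure of 4 counts Study A only, provided Study B enrolment is additional to the target. Section 9.6 also analyses everyone enrolled, up to 34 + 20 = 54 in Phase 3, or about 27 per arm if allocation is 1:1. A class time and its instructor can also outlast any one set of members.

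Finally, the design-effect formula is only approximate for overlapping classes, and it does not correct the degrees of freedom when classes are few. That is a fair limit on the remedy and should be stated with it.

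**Conclusion.** The point holds conditionally. The documents establish shared classes in both arms, and t-tests and intervals with no allowance for class or instructor. For any positive correlation among class-mates' change scores, the stated intervals under-cover. How much cannot be settled from the documents. With an assumed ICC of 0.02 to 0.10, the standard error should be about 3% to 14% larger at 4 teens per cluster and 7% to 32% larger at 8.5. It would be 15% to 61% larger only if one class time per arm behaves as a single lasting cluster of 17.

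The sample size of 34 is untouched, because no power calculation lies behind it. The feasibility and acceptability targets in Table 5 do not use these intervals. This is a correction to how exploratory precision is reported, not a flaw in the primary aim.

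**What to change.** - Record class time and instructor or therapist for each teen with the attendance data. Section 6.2.3 already places dates of sessions attended in the non-blind database, so the addition is small. Keep it there until database lock so that the blind is not affected.
- Beside each within-arm confidence interval, report a sensitivity interval widened by √(1 + (m − 1) × ICC) at ICC 0.02, 0.05 and 0.10. Take m from realised class membership among the teens in that analysis, and note that the result is approximate under rolling entry and with few classes.
- Label the unadjusted interval as ignoring class and instructor clustering.
- Note in section 9.6 that if these estimates are used to plan the full trial, the planning should include an explicit ICC.

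The cost is a few lines of analysis and one extra field per teen, with no new assessments and no change to the sample size. The downside is that the exploratory intervals become wider and the widened ones rest on an assumed ICC.
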